2.5.6 Supplementary analyses

An additional supplementary analysis will be performed if the percentage of participants using prohibited concomitant medications for the intent to treat SMA (i.e., nusinersen and risdiplam) is more than 5% (≥ 7 participants) in FAS. The supplementary estimand will be similar to the primary estimand except that the treatment policy strategy will be used (instead of the hypothetical strategy) to handle the intercurrent event of use of prohibited concomitant medications for the intent to treat SMA.

2.6 Analysis supporting secondary objectives

2.6.1 Secondary endpoint(s)

The secondary endpoints are as follows:

1. Change from baseline in HFMSE total score at the end of Follow-up Period 1 for participants aged ≥ 2 to < 5 years
2. Achievement of at least a 3-point improvement from baseline in HFMSE total score at the end of Follow-up Period 1 (responders) for participants aged ≥ 2 to < 18 years
3. Achievement of at least a 3-point improvement from baseline in HFMSE total score at the end of Follow-up Period 1 in the ≥ 2 to < 5 years age group
4. Change from baseline in RULM total score at the end of Follow-up Period 1 for participants aged ≥ 2 to < 18 years
5. Change from baseline in RULM total score at the end of Follow-up Period 1 for participants aged ≥ 2 to < 5 years

2.6.2 Statistical hypothesis, model, and method of analysis

The continuous secondary endpoints of change from baseline in HFMSE and RULM scores in the younger age group or the whole study population will be analyzed in a similar manner to how the primary endpoint will be analyzed. The continuous HFMSE endpoint will include baseline HFMSE total score as a covariate in the model and the continuous RULM endpoints will include baseline RULM total score as a covariate in the model. Line plots will be produced for each of the continuous secondary endpoints to display the LSMS for each treatment group and associated 95% CIs at each visit through the end of Follow-up Period 1.

The dichotomous endpoint (proportion of responders, defined as participants who achieve at least a 3-point improvement from baseline in HFMSE total score at the end of Follow-up Period 1) will be analyzed by a Generalized Linear Mixed Effects model including treatment, CCI

[figure not shown]
The model will include “logistic” as the link function with unstructured (UN) covariance matrix.

In case of non-convergence of the above model, the endpoint will still be analyzed by a Generalized Linear Mixed Effects model with the covariance matrix changed to compound symmetry (CS). In case the model does not converge even then, the dichotomous endpoint will be analyzed by a logistic regression model including treatment, strata and the baseline HFMSE total score as covariate (if quasi-complete separation issue like 0 responders in sham group is encountered, “firth” correction will be applied to obtain the odds ratio, 95% CI and corresponding p-value). In this case, the proportion of responders and corresponding 95% CIs at each visit will be displayed and the odds ratio of OAV101 compared to sham group with associated 95% CIs and two-sided p-values will be provided for the End of Follow-up Period 1.

In all cases, estimates (difference or odds ratio) of OAV101 arm compared to sham group with associated 95% CIs and two-sided p-values will be provided.

Testing Procedure

CCI

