1.2.2 Secondary estimand(s)

The secondary estimand for the continuous secondary efficacy endpoints is defined similarly to the primary estimand.

The secondary estimand for the dichotomous secondary efficacy endpoint (i.e., achievement of at least a 3-point improvement from baseline in HFMSE total score at the end of Follow-up Period 1) is described by the attributes listed below.

1. Population of interest: Sitting but never ambulatory patients aged ≥ 2 to < 18 years with Type 2 SMA.
2. Endpoint: Proportion of participants achieving at least a 3-point improvement from baseline in HFMSE total score at the end of Follow-up Period 1.
 - CCI
[REDACTED]
 - Summary measure: odds ratio between treatment groups for the proportion of participants achieving at least a 3-point improvement from baseline in HFMSE total score at the end of Follow-up Period 1.
3. Treatment of interest: The randomized treatment (OAV101 or sham procedure) with or without the use of prohibited concomitant medications not for the intent to treat SMA.

Handling of intercurrent events:

1. Study discontinuation due to reasons other than death: It is assumed that participants discontinuing the study prior to Week 52 would follow the same trend as participants who continued and remained in the study for the full 52 weeks. Data collected up to the point of discontinuation will be included in the Generalized Linear Mixed Effects Model (Hypothetical strategy).
2. Use of prohibited concomitant medications not for the intent to treat SMA: Assessments collected while/after receiving prohibited concomitant medications not for the intent to treat SMA will be included in the analyses (Treatment policy strategy).
3. Use of prohibited concomitant medications for the intent to treat SMA (i.e. nusinersen, risdiplam): Assessments collected while/after receiving prohibited concomitant medications for the intent to treat SMA will not be included in the analyses. Only data collected up to the point of initiating a prohibited medication for the intent to treat SMA will be included in the Generalized Linear Mixed Effects Model and the data collected after the initiation of prohibited medication for the intent to treat SMA will be considered as missing (Hypothetical strategy).

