2.6.4 Handling of missing values not related to intercurrent event

The primary analysis method, MMRM or Generalized Linear Mixed Effects Model (depending on the endpoint being analyzed), implicitly imputes missing data under a missing at random assumption.

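### The responder odds ratio's missing-data handling, and possibly its scale, depend on which model converges; the last fallback drops participants with no Week 48 or Week 52 score

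*SAP*

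**What the plan says.** - **Estimand.** SAP 1.2.2 (likewise Protocol 2.2) sets the summary measure as the "odds ratio between treatment groups for the proportion of participants achieving" the 3-point gain at End of Follow-up Period 1. For participants who leave the study, observations up to the time "of discontinuation will be included in the Generalized Linear Mixed Effects Model". SAP 2.6.3 repeats this. Scores after starting nusinersen or risdiplam are treated as missing, and deaths receive the participant's worst score.
- **Model sequence.** In SAP 2.6.2 the first choice is a generalized linear mixed effects model with the logit "as the link function with unstructured (UN) covariance matrix". If it does not converge, the matrix becomes compound symmetry. If that also fails, "the dichotomous endpoint will be analyzed by a logistic regression model including treatment, strata and the baseline HFMSE total score as covariate", with a Firth correction for separation; the odds ratio and "two-sided p-values will be provided for the End of Follow-up Period 1". Part of the sentence listing the mixed model's terms is redacted.
- **Missing data.** SAP 2.6.4 says that the MMRM or the mixed model "implicitly imputes missing data under a missing at random assumption". It does not name the logistic step.
- **Endpoint value.** SAP 2.1.1 averages Weeks 48 and 52, or takes whichever one is available. With neither, there is no value.
- **Safety net.** SAP 2.5.5, extended to secondary endpoints by 2.6.5, runs multiple imputation only if more than 5% of the FAS (7 or more participants) lack the end-of-period HFMSE. SAP 5.1.4.1 gives the steps.

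**The concern.** The plan has one responder estimand but three estimators, and convergence decides which is reported. They differ in two ways.

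First, the logistic step uses a single time point and carries no imputation rule. Anyone with neither a Week 48 nor a Week 52 score falls out of it, and that participant's earlier visits go unused. That departs from SAP 1.2.2 and 2.6.3, and the missing-at-random statement in 2.6.4 does not extend to this step.

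Second, the odds ratio may not be on the same scale at each step. If the mixed model has random effects, its treatment coefficient is a subject-specific odds ratio, which is not the ratio of odds of the two group proportions. If it models residual covariance, the odds ratio does not condition on a random effect, but the fit is by quasi- or pseudo-likelihood, so validity under missing at random is not guaranteed.

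What is at stake is the meaning of the reported effect size and the handling of missing data for two responder endpoints (overall and age 2 to under 5). Power is not in question.

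**Working it through.** **Inputs from the documents.** Responder rates 75% OAV101 and 13% sham; 39 and 26 participants in the younger group; alpha 0.05 (SAP 3). Planned totals 75 and 50 (SAP 1.1). Thirteen post-baseline HFMSE visits, Weeks 4 to 52 (SAP 2.1.2).

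**Assumptions, because the documents give no figures.** Random-intercept SD 1 to 3 (latent intraclass correlation 0.23 to 0.73); missingness 5% to 30% per arm.

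**1. The plan's own figure.** For 75% v 13% with 39 v 26, two-sided 0.05, power is 99.99% by the normal approximation and 99.97% by Fisher's exact test. The stated figure of more than 99% is reproduced.

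**2. The estimand at the planning rates.** (0.75/0.25) / (0.13/0.87) = 20.1.

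**3. The random-effects reading.** For each arm, solve for b so that the average of expit(b + SD × z) over a standard normal z equals that arm's response rate. The subject-specific odds ratio is exp(b_OAV101 − b_sham).

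| Random-intercept SD | Subject-specific OR | Log OR relative to marginal |
|---|---|---|
| 1 | 34.8 | 1.18 |
| 1.5 | 61.2 | 1.37 |
| 2 | 118.8 | 1.59 |
| 3 | 529.8 | 2.09 |

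This gap needs no missing data. In simulated data, integrating the random effect out returned 18.6 to 19.9, against 19.2 to 19.9 with full data.

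**4. The logistic step.** Large-sample simulation (12,000 to 20,000 participants, 12 time points, no covariates) of dropout driven by the last observed responder status. With autoregressive latent correlation 0.9 or 0.95, and non-responders five times as likely to leave in the second half of follow-up:

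| Missing OAV101 / sham | Full-data OR (0.9; 0.95) | Logistic on those observed (0.9; 0.95) |
|---|---|---|
| 5% / 5% | 19.2; 20.3 | 19.5; 20.8 |
| 20% / 5% | 19.2; 20.3 | 22.4; 25.1 |
| 5% / 30% | 19.2; 20.3 | 17.0; 18.0 |

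With data generated from a random intercept (SD 2; 3), the 20% / 5% case gave a smaller shift: 20.4 v 19.2 and 22.0 v 19.9.

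**5. The residual-covariance reading.** A compound-symmetry GEE, standing in for this model, gave 18.4 to 19.2 against 19.2 at correlation 0.9, and 19.9 to 20.7 against 20.3 at 0.95, over the same range of dropout.

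**6. The imputation trigger.** 5% of 125 = 6.25, hence 7. Six missing overall is 6/125 = 4.8%. If all six are in the younger group, that is 6/65 = 9.2%; if all are also on OAV101, 6/39 = 15.4% of that arm. Neither case triggers the check.

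**7. Whether the fallbacks could be reached.** An unstructured matrix over T visits has T(T+1)/2 parameters: 91 for 13 visits, 78 for 12 if Weeks 48 and 52 are merged, with 125 or 65 participants. With random effects the count may be only 1 (intercept) or 3 (intercept and slope). In the younger group 26 × 0.13 = 3.4 sham responders are expected, and the chance of none is 0.87^26 = 2.7%.

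**The case against.** The strongest reply is that the model sentence in SAP 2.6.2 is redacted just where random effects, a residual structure or a marginalization step would be named, so nothing can be called missing from the mixed model. That stands: the scale point is conditional, and the parameter count in item 7 shows only that the fallbacks are possible.

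The fallback order is also fixed in advance, with a Firth correction, so no analyst picks by result. Withdrawal is planned to be minimal, and at 5% missing per arm the shift is trivial. The logistic step omits only participants with neither score, deaths are imputed, and it remains valid if missingness depends only on treatment, strata and baseline. The scenarios with a sizeable shift would exceed the 7-participant trigger: 20% of 75 is already 15. All of this stands. Even so, the imputed result would then be a sensitivity analysis beside a headline odds ratio that ignored the dropouts' visits, and six losses concentrated in the younger group would trigger nothing.

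A reader might infer more than the documents support:
- That SAP 2.6.4 is contradicted. It speaks only of the MMRM and the mixed model.
- That missing at random fails under residual covariance. It is only not guaranteed, and the simulated shift was at most about 4% (18.4 v 19.2).
- That a larger subject-specific odds ratio raises the false-positive rate. With no treatment effect and the same random-effect distribution in both arms, both odds ratios equal 1.

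**Conclusion.** The departure from the estimand is in readable text: the last fallback does not use visits before discontinuation, and no missing-data rule covers it. Its size depends on dropout. It is negligible when dropout is minimal. At an assumed 20% OAV101 / 5% sham missing, the odds ratio was 22 to 25 instead of 19 to 20 under the autoregressive assumptions, less under a random-intercept mechanism, and it fell below the full-data value when sham losses were the larger. The simulations had no covariates, so baseline and strata could absorb part of this.

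The change of scale is conditional on redacted text. If random effects are used, the coefficient would be about 35 to 530 for SD 1 to 3, against a marginal 20. That concerns how the effect is read. The documents do not show the responder test to be invalid, nor that the fallbacks will be needed. The testing procedure is redacted, so the endpoints' place in it cannot be confirmed here.

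**What to change.** 1. In SAP 2.6.2, replace the last fallback with the analysis already set out in SAP 5.1.4.1, at any level of missingness: impute the visit HFMSE scores under missing at random, average Weeks 48 and 52, derive responder status, fit logistic regression with treatment, strata and baseline (Firth if separated), and pool.
2. Whichever step is used, report standardized responder proportions by arm and their odds ratio. With random effects this means integrating them out. With logistic regression it means averaging over strata and baseline, because the covariate-adjusted odds ratio is itself conditional. The reported quantity then matches SAP 1.2.2 and does not change scale with convergence.
3. If the redacted wording does not already do so, state whether the covariance belongs to random effects or residuals, and the estimation method.

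The cost is SAP wording and a little more programming: the combining step in 5.1.4.1 describes only least squares means and treatment differences, so pooling of the log odds ratio must be added. The reported odds ratio may look smaller than a subject-specific one. Making imputation plus logistic regression the primary responder analysis is an option, not a requirement.

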2.6.3 Handling of intercurrent events

The same methodology for handling of intercurrent events as described for the primary endpoint will be applied to the secondary endpoints:

1. Study discontinuation due to reasons other than death: It is assumed that participants discontinuing the study prior to Week 52 would follow the same trend as participants who continued and remained in the study for the full 52 weeks. Data collected up to the point of discontinuation will be included in the MMRM/Generalized Linear Mixed Effects Model (Hypothetical strategy).
2. Use of prohibited concomitant medications not for the intent to treat SMA: Assessments collected while/after receiving prohibited concomitant medications not for the intent to treat SMA will be included in the analyses (Treatment policy strategy).

3. Use of prohibited concomitant medications for the intent to treat SMA (i.e. nusinersen, risdiplam): Assessments collected while/after receiving prohibited concomitant medications for the intent to treat SMA will not be included in the analyses. Only data collected up to the point of initiating a prohibited medication for the intent to treat SMA will be included in the MMRM/Generalized Linear Mixed Effects Model and the data collected after the initiation of prohibited medication for the intent to treat SMA will be considered as missing (Hypothetical strategy).
4. Study discontinuation due to death: The worst score for HFMSE/RULM will be imputed for participants who discontinue the study due to death, and this imputed score will be utilized in the analysis. The “worst score” refers to the worst (lowest) HFMSE/RULM score collected for the participant who had the death event throughout the trial (considering both the baseline and post-baseline period). It is anticipated that this intercurrent event is unlikely to occur during this study.

2.6.4 Handling of missing values not related to intercurrent event

The primary analysis method, MMRM or Generalized Linear Mixed Effects Model (depending on the endpoint being analyzed), implicitly imputes missing data under a missing at random assumption.

2.6.5 Sensitivity analyses

The same methodology for sensitivity of the primary endpoint will be applied to the secondary endpoints.

Additionally, another sensitivity analysis will be performed for the RULM secondary endpoints. The RULM has been validated in SMA patients 30 months of age to adults. Therefore, subjects whose age at screening visit 1 was < 30 months of age will be excluded from this analysis.

2.6.6 Supplementary analyses

No supplementary analysis is planned.

2.7 Safety analyses

Safety will be assessed through the incidence and severity of TEAEs, vital sign assessments, cardiac assessments (echocardiogram [ECHO], ECG), laboratory evaluations (chemistry, hematology, immunology, urinalysis), physical/neurological examinations, suicidal ideation and behavior, anthropometry, and use of concomitant medications. TEAEs will be coded in accordance with the most current version of the MedDRA coding dictionary. The actual version of the MedDRA coding dictionary used will be noted in the summary tables and in the clinical study report. All summaries of safety data will be based on the SAF, unless otherwise specified.

Safety summaries (tables, figures) will include only data from the on-treatment period with the exception of baseline data which will also be summarized where appropriate (e.g. change from baseline summaries). The on-treatment period lasts from the date of first administration of study treatment to completion of the study at Week 64. Separate summaries will be produced

considering data through the end of Follow-up Period 1, and separately through the end of Follow-up Period 2.

2.7.1 Adverse events (AEs)

An overview summary table of AEs reported through the end of Follow-up Period 1 will be presented by Treatment Period 1 treatment group (OAV101, sham), consisting of the number and percentage of participants experiencing at least one event for each of the following categories:

- Any TEAE
- Any TEAE related to study treatment
- Any serious TEAE
- Any serious TEAE related to study treatment
- Any severe TEAE
- Any TEAE leading to discontinuation from study
- Any TEAE leading to death
- Any AESI (refer to [Section 2.7.1.1](#) of this SAP)

The number and percentage of participants with TEAEs will be summarized in the following ways:

- by treatment group, primary SOC, and PT along with the total number of events
- by treatment group, primary SOC, PT, and maximum severity

Separate summaries by Treatment Period 1 treatment group (OAV101, sham), primary SOC, and PT will be provided for TEAEs leading to death, TEAEs related to study treatment, TEAEs related to prednisolone/placebo, serious TEAEs, serious TEAEs related to study treatment, TEAEs leading to discontinuation from study, non-serious TEAEs reported in >5% of participants, and AESIs.

Additionally, separate summaries by Treatment Period 1 treatment group (OAV101, sham) and PT will be provided for TEAEs, TEAEs related to study treatment and serious TEAEs.

All information obtained on AEs through the end of study will be listed by Treatment Period 1 treatment group (OAV101, sham) and participant.

The number and percentage of participants with TEAEs reported within 72 hours of treatment with the study treatment will be summarized by treatment group, primary SOC and PT.

A similar, second set of outputs will be produced to summarize the TEAEs reported after dosing with OAV101 and through the end of Follow-up Period 2 using OAS. In this second set of outputs, only TEAEs reported on/after OAV101 dosing (during Treatment Period 1 and through the end of study for participants originally randomized to OAV101, during Treatment Period 2 and through the end of study for participants originally randomized to sham administration) will be considered.

For the legal requirements of ClinicalTrials.gov and EudraCT, two required tables on TEAEs which are not serious adverse events with an incidence > 5% and on treatment emergent serious

adverse events and SAE suspected to be related to study treatment will be provided by system organ class and preferred term based on the SAF.

If for a same patient, several consecutive AEs (irrespective of study treatment causality, seriousness and severity) occurred with the same SOC and PT:

- a single occurrence will be counted if there is \leq 1 day gap between the end date of the preceding AE and the start date of the consecutive AE
- more than one occurrence will be counted if there is $>$ 1 day gap between the end date of the preceding AE and the start date of the consecutive AE

SOCs will be presented in alphabetical order and the PTs will be presented by descending number of participants with events in OAV101 within each SOC.

For occurrence, the presence of at least one SAE / SAE suspected to be related to study treatment / non SAE has to be checked in a block e.g., among AE's in a \leq 1 day gap block, if at least one SAE is occurring, then one occurrence is calculated for that SAE.

The number of deaths resulting from SAEs suspected to be related to study treatment and SAEs irrespective of study treatment relationship will be provided by SOC and PT.

2.7.1.1 Adverse events of special interest / grouping of AEs

On the basis of important identified or potential risks associated with OAV101, AESIs are determined and categorized as follows. These will be summarized and listed based on Standardized MedDRA terminology:

- Hepatotoxicity
- Transient thrombocytopenia
- Cardiac adverse events
- Dorsal root ganglia toxicity
- Thrombotic microangiopathy
- New malignancies

AESIs will be identified using Novartis electronic Case Retrieval Strategy (eCRS).

Thrombotic microangiopathy will be identified via the following PTs: thrombotic microangiopathy OR haemolytic uraemic syndrome OR atypical haemolytic uraemic syndrome.

2.7.2 Deaths

Deaths will be presented in both a data listing and a summary table for AEs with fatal outcome, including cause of death and other details such as autopsy if given. All data will be considered for analysis up to the time of death.

2.7.3 Laboratory data

Safety laboratory data and genetic diagnosis laboratory data analyzed by both the central laboratory as well as by local labs will be utilized for safety analyses. The SAF will be used for all summaries of data.

Values at each scheduled visit as well as change from baseline values to each post-baseline visit through the end of Follow-up Period 1 will be summarized for each protocol-specified chemistry, hematology, and liver function test laboratory parameter using descriptive statistics for Treatment Period 1 treatment group (OAV101, sham). Normalized values (observed absolute values/ULN) for ALT, AST, ALP, total bilirubin and troponin-I and absolute values for platelets at each scheduled visit as well as change from baseline in absolute values to each post-baseline visit through the end of Follow-up Period 1 will be visualized on a box plot. Listings of hematology (all platelet values and out of range values for all other parameters), chemistry (out of range values for all parameters), urinalysis (out of range values for all parameters), and hepatic laboratory data meeting elevation criteria data will also be produced. Listings of liver imaging, if performed will also be produced.

In addition, shift tables based on CTC grade (CTCAE version 5) will be provided for all laboratory parameters that were defined in the [\[Novartis Internal Guidance on CTCR Grading of Lab Parameter\]](#) (e.g., platelets, alanine aminotransferase (ALT), aspartate aminotransferase (AST), alkaline phosphatase (ALP), gamma glutamyl transferase, and serum total bilirubin, etc.) to compare a participant's baseline laboratory evaluation relative to the post-baseline values. For laboratory (serum) parameters Glutamate Dehydrogenase and Troponin I, shift tables will be produced by below, within, or above the normal range level based on normal ranges of the laboratory used in this study (Low/Normal/High).

The shift tables will cross tabulate the frequency (number and percentage) of participants with baseline versus post-baseline level. These summaries will be presented by laboratory test and treatment group for overall. The shift tables will present shifts from baseline to each visit and to final value. Moreover, for laboratory parameters based on CTC grade, shift tables from baseline to the worst CTC grade level at any time post-baseline will be generated. Participants with specific laboratory abnormalities (defined by CTC grade 3 and 4) will be listed. For laboratory parameters based on Low/Normal/High range, shift tables from baseline to the maximum at any time post-baseline will be generated.

A second set of shift tables will be produced to summarize the shifts from baseline to the maximum value, and final values as well as shift tables based on CTCAE grades from baseline to worst post-baseline values reported after treatment with OAV101. In this second set of outputs, only laboratory values reported on/after OAV101 dosing (during Treatment Period 1 and through the end of study for participants originally randomized to OAV101, during Treatment Period 2 and through the end of study for participants originally randomized to sham administration) will be considered.

The number and percentage of participants meeting each of the following criteria through the end of Follow-up Period 1 will be summarized:

- Alanine aminotransferase (ALT) >2x upper limit of normal (ULN), ALT >3x ULN, ALT >5x ULN, ALT >8x ULN, ALT >10x ULN, ALT >20x ULN
- Aspartate aminotransferase (AST) >2x ULN, AST >3x ULN, AST >5x ULN, AST >8x ULN, AST >10x ULN, AST >20x ULN
- ALT or AST >2x ULN, ALT or AST >3x ULN, ALT or AST >5x ULN, ALT or AST >8x ULN, ALT or AST >10x ULN, ALT or AST >20x ULN

- Total bilirubin $>1.5 \times$ ULN, $>2 \times$ ULN, Total bilirubin $>3 \times$ ULN
- ALT or AST $>3 \times$ ULN and Total bilirubin $>2 \times$ ULN
- ALT or AST $>3 \times$ ULN and Total bilirubin $>2 \times$ ULN and Alkaline phosphatase (ALP) $\geq 2 \times$ ULN
- ALT or AST $>3 \times$ ULN and Total bilirubin $>2 \times$ ULN and ALP $<2 \times$ ULN

A participant or event will be counted if the post-baseline laboratory values meet the above criteria regardless of the baseline laboratory value (i.e., the post-baseline laboratory value does not need to be worse than the baseline laboratory value). For the last three combination categories, the values do not need to have been collected at the same assessment. For participants meeting any elevation criterion, a corresponding listing of all ALT, AST, ALP, INR, GLDH and total, direct, and indirect bilirubin values will be provided.

Additionally, a summary will be produced to detail the number and percentage of participants with post-baseline, post-OAV101 treatment values meeting the specified criteria outlined above. In this second summary, only laboratory values reported on/after OAV101 dosing (during Treatment Period 1 and through the end of study for participants originally randomized to OAV101, during Treatment Period 2 and through the end of study for participants originally randomized to sham administration) will be considered.

